Inclusion criteria: Men living with HIV must meet the following criteria: (a) aged ≥ 18 years; (b) previously receiving HIV care at the study clinic; (c) missed their most recent ART clinic appointment by >28 days, (d) not planning to relocate to another region within the next 12 months; (e) able and willing to provide informed consent; (f) not currently taking ART. Importantly, agreement to be contacted by a coach (if selected) is not an eligibility criterion as our goal is to obtain generalizable evidence of the overall effectiveness of the Coach Mpilo program (uptake of communication with coaches will be explored in Aim 2).

Consenting process: Study staff will review the informed consent form with men who meet the inclusion criteria and answer any questions that men may have about study participation. The consent form (see Appendix A) includes a brief description of the Coach Mpilo intervention and the goals of the study. Staff will also obtain consent to review clinic records for participants. Those who provide informed consent and meet criteria for enrollment will proceed to randomization.

Data collection

Baseline survey: Study staff will administer a baseline questionnaire to obtain information on, among other things, participants' demographic characteristics, socio-economic status, health behaviour (HIV testing history, sexual behaviour, alcohol use), future outlook, internalized stigma and mental health. The baseline survey is found in Appendix B.

Follow-up survey: Study staff will contact participants at six months and administer an in-person

follow-up survey; many of the questions administered at baseline will be assessed again. The follow-up survey is found in Appendix C.

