Clinic records: We will obtain participants' health outcome data from electronic clinic data via TIER.Net (South Africa's national electronic HIV/TB monitoring system), to assess individual- and facility-level outcomes related to HIV. Where necessary for confirmation we will also retrieve data from physical clinic files. With consent from participants, we will use the participants folder number to match to their Tier.Net data at the clinic or subdistrict level. In cases of missing, mismatched, or duplicate folder numbers, fallback matching strategies may be applied using combination variables such as names, mobile phone number, year of birth, and only within data security constraints. We will conduct periodic validation and deduplication processes to improve linkage accuracy and reduce error. In addition, participants' data on laboratory tests relevant for HIV care (including viral load tests) will be requested from the National Health Laboratory Services (NHLS). All data will be handled in accordance with ethics approvals and national data protection standards. The study team will report linkage rates and assess potential bias due to non-linkage in the final analysis.

Coach Log Book: To collect data on the engagement between coaches and their clients, the coaches will maintain a log book of the dates, duration and mode (e.g., in-person, telephone call, WhatsApp messages) of contact with clients.

Randomization: Following the baseline survey, participants will be randomized (1:1) to a control group that receives the SOC and an intervention group that receives SOC plus the Coach Mpilo intervention. For the SOC, participants will receive the standard in-person tracking and tracing support as per the South African National Guidelines for individuals living with HIV who have missed clinic appointments. For the intervention group, participants will be informed about the potential support from a Coach. They will be provided with the details of their assigned coach and contact details for them to reach out to the Coach. In addition, permission will be obtained to provide their contact details to the Coach so that the Coach can initiate contact with them.

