Outcomes: The primary outcome will be retention in HIV care at 12 months, defined as attending a follow-up clinic visit on or before 12 months and obtaining adequate ART refills for a supply of medications at 12 months post study enrolment. Studying this outcome will address an important question about whether time-limited, resource-intensive interventions like Coach Mpilo have a durable effect on participants' health outcomes. The outcome also features prominently in cost-effectiveness modeling that we will undertake.

Secondary outcomes will include retention in care at 6 months; viral suppression (<50 copies/ml) at 6 and 12 months; and adherence over 6 and 12 months using proportion of days covered (PDC). In addition, we will examine outcomes measured in the 6-month follow-up survey: HIV-status disclosure, mental health, internalized stigma, self-esteem, employment and social isolation.

Analyses: Primary analysis: We will conduct intention-to-treat analysis and estimate a logistic regression model that includes clinic fixed effects and month of enrollment, and controls for baseline participant characteristics that are significantly different between study groups.

Secondary analyses: We will repeat the primary analyses for each secondary outcome. Analysis of six-month outcomes will indicate whether Coach Mpilo has promising immediate effects on participants' health and well-being. Analyses of outcomes such as mental health, social isolation, and future orientation will provide insights on potential mechanisms by which the Coach Mpilo intervention may affect men's health.

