Sample size and power calculations: We determined the target sample size based on statistical power to detect a clinically relevant effect of the intervention on the primary outcome of retention in care. We anticipate that Coach Mpilo will increase re-engagement and retention in HIV care (the primary outcome) by 10 percentage points. The Coach Mpilo pilot study found that 88% of men with coaches missed no clinic visits in their first seven months on ART, and 95% of men remained in care at seven months. This indicates 18-25% higher retention in care compared to several studies in South Africa that have found 30% drop out of care in the first six months of treatment.^{2,4,5} Given potential biases in the pilot data - there was no control group, data was self-report and not disaggregated by engagement in care at baseline - we hypothesize the intervention will increase retention in care by at least 10 percentage points. We performed power calculations under varying scenarios of the primary outcome in the control group. Based on existing data from clinics and prior research, we anticipate retention in care at 12 months to be 40-60%.^{12,13} With a sample size of 786 participants and 50% retention in care at 12 months, we will have 80% power to detect a difference of 10 percentage points between study groups. As a result, we will aim to recruit about 800 participants in the Aim 1 trial.

We also anticipate the intervention to: 1) improve mental health by reducing internalised stigma, increasing social support, and increasing hope; 2) reduce fears associated with living with HIV; 3) encourage HIV status disclosure.

Aim 2: Identify the populations of men who are *not* reached by and do not respond to Coach Mpilo

In the intervention group, we will measure intervention uptake and amount of engagement participants have with a coach. Primary quantitative analysis will assess the determinants of uptake within the intervention group to advance the limited evidence on sub-groups that are typically missed by peer-led interventions and therefore require different types of support. Qualitative interviews will also be conducted to better understand program uptake and engagement with a coach.

Participants: Aim 2 will be conducted with data collected from coaches and from Aim 1 trial participants.

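### Participant-level covariates enter the primary model only if they differ significantly between arms, so chance rather than prognosis chooses them and the model is not fixed in advance

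*Protocol*

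**What the plan says.** The Analyses paragraph under Aim 1 says the team will "estimate a logistic regression model that includes clinic fixed effects and month of enrollment", and that the model also "controls for baseline participant characteristics that are significantly different between study groups". Clinic and month are therefore fixed in advance; participant characteristics are conditional on a comparison between arms. The protocol names no participant characteristic that is always included, and gives no candidate list, no test and no significance level for the comparison. The same analysis is then to be run for every secondary outcome.

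Three other places bear on this:

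- **Randomization:** "Following the baseline survey, participants will be randomized (1:1) to a control group". Allocation is individual and follows the baseline survey.
- **Baseline survey:** it collects "among other things, participants' demographic characteristics, socio-economic status, health behaviour (HIV testing history, sexual behaviour, alcohol use), future outlook, internalized stigma and mental health". The list is open-ended.
- **Outcomes, and Sample size and power calculations:** "The primary outcome will be retention in HIV care at 12 months", a binary outcome, and the planned effect is on the percentage-point scale: "detect a difference of 10 percentage points between study groups".

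**The concern.** When individuals are randomised properly, any significant baseline difference is a chance finding. Testing it does not show whether the variable predicts retention, and predicting the outcome is what makes adjustment worthwhile. A rule based on such tests leaves out strong predictors that happen to be balanced and lets in irrelevant variables that happen not to be.

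Because the list, the test and the threshold are all open, the primary model cannot be written down until baseline data have been compared by arm. Two analysts could follow the protocol faithfully and fit different models. An SAP that followed the clause would inherit the problem. At stake are the prespecification of the confirmatory analysis and some precision that could be had at almost no cost.

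**Working it through.** **1. The plan's own sample size.** For a gap of 10 percentage points, the protocol states "With a sample size of 786 participants and 50% retention in care at 12 months, we will have 80% power to detect a difference of" that size. Alpha is not stated; I take two-sided 5%. With variance 0.25 in both arms:

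n per arm = 2 × 0.25 × (1.960 + 0.842)² / 0.10² = 392.6 with these rounded quantiles, so 393, or 786 in total.

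The figure reproduces exactly (power 0.801). The pooled two-proportion formula for 50% versus 60% gives 776 in total, and power 0.806 at 393 per arm. The calculation uses no covariates, so the clause does not affect it.

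**2. How often the rule selects something.** At an assumed 5% level, each characteristic enters with probability 0.05 whatever its relation to retention, and is left out with probability 0.95. For k independent candidates, P(at least one selected) = 1 − 0.95^k and the expected number selected is 0.05k. The protocol does not give k.

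| k | P(at least one) | Expected number |
|---|---|---|
| 5 | 23% | 0.25 |
| 10 | 40% | 0.5 |
| 15 | 54% | 0.75 |
| 20 | 64% | 1.0 |
| 30 | 79% | 1.5 |

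Independence is a simplification, since scales such as stigma, mental health and future outlook are probably correlated. Correlation changes the middle column but not the 5% entry rate of each variable or the expected number.

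**3. Type I error under the rule.** Simulated trials: 800 men, 1:1, 15 independent candidates, 8,000 replicates per scenario, no treatment effect. The rejection rate was 0.051 with one prognostic covariate (log-odds 0.8 per SD) and 0.045 with three (0.8, 0.5, 0.5). Across the null and non-null runs, the strongest predictor was selected in 4.7% to 5.3% of trials.

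**4. Power.** Marginal retention 50% versus 60%, 800 men.

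| Assumed prognostic covariates (log-odds per SD) | Under the rule | Always included | Gain |
|---|---|---|---|
| Three at 0.6 | 0.82 | 0.89 | 7 points |
| Three at 0.4 | 0.80 | 0.84 | 4 points |
| Three at 0.2 | 0.81 | 0.82 | 1 point |
| One at 0.8 | 0.82 | 0.86 | 4 points |
| Three at 0.8, 0.5, 0.5 | 0.82 | 0.88 | 6 points |

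The first three rows have 20 candidates, clinic and month in every model, and 2,500 runs. The Monte Carlo standard error of one power estimate is √(0.8 × 0.2 / 2,500) = 0.008, so the one-point gain is about the size of simulation error. The last two rows have 15 candidates, no clinic or month terms, and 8,000 runs. In those two scenarios power with no participant covariates was 0.816 and 0.809, against 0.820 and 0.817 under the rule. The rule therefore gains almost nothing over leaving participant covariates out.

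**5. Effect of the open threshold.** In further runs of 3,000 trials with a true effect, moving the selection level from 5% to 10% changed the significance verdict in about 2% of trials.

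**6. Effect on the odds ratio.** With three covariates at 0.6 per SD, the mean treatment log-odds ratio was 0.413 with no participant covariates and 0.418 under the rule. The shift is 0.418 − 0.413 = 0.005, against a sampling SD of 0.14.

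**The case against.** The best defence is that the rule does little harm. It looks only at baseline data, never at outcomes. Clinic and month of enrolment are in every model. Type I error holds, the sample size is sound, and admitting an irrelevant covariate with 800 men costs almost nothing. All of that stands, and it is why this is an improvement to make and not a fault that undermines the trial.

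It can also be said that an SAP may supply the list. It may, but the protocol does more than leave the list open: it states the selection criterion, and that criterion is the problem.

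Four stronger readings are tempting and are not supported:

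- *That the primary model has no fixed covariates.* Two terms are prespecified; the rule governs participant characteristics only.
- *That the test is biased or the trial underpowered.* The simulations show neither.
- *That the effect being estimated swings materially with chance imbalance.* An odds ratio does depend in principle on the covariates in the model, but the average shift under the rule is about 0.005 on the log scale.
- *That the trial will report an odds ratio at odds with its percentage-point planning and the Aim 3 cost per additional person retained.* The protocol names a logistic model, not the reported summary measure, and such a model can yield a risk difference.

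**Conclusion.** The point holds in this limited form and should be fixed. The clause selects participant covariates by chance imbalance, omits any given prognostic variable about 95% of the time (assumed 5% level), and leaves the primary and secondary models undetermined until the arms are compared.

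The cost is a model that is not prespecified and a forgone power gain of about 1 to 7 points. That range depends wholly on assumed inputs: three independent prognostic covariates at log-odds 0.2 to 0.6 per SD, 800 men, and 50% versus 60% retention. The protocol gives no prognostic strengths, number of candidates or selection level. The case for change rests more on prespecification than on power.

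**What to change.** Delete the significance-based clause and keep clinic and month of enrolment. Name a short list of baseline covariates expected to predict retention, and include them whatever their balance. Candidates already covered by the baseline survey are age, socio-economic status, alcohol use, internalised stigma and mental health. Days overdue at enrolment could be added if it can be derived from clinic records; the protocol does not say it is collected. The document does not show which of these predict retention, so the choice is for the investigators.

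The list should be fixed before any outcome or by-arm data are examined. The protocol describes no masking, so an unblinding date cannot serve as the milestone.

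Optionally, report the standardised risk difference with its 95% confidence interval from the same model, because the planned effect and the Aim 3 incremental cost are both on that scale.

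The cost is about one sentence in the protocol, mirrored in the SAP, with no new survey data and no change to the sample size.

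### Repeating the primary logistic analysis for each secondary outcome gives undichotomised survey scores a binary model and usually leaves out the baseline stigma and mental health scores

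*Protocol*

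**What the plan says.** Under Aim 1, Analyses, the Protocol defines the primary analysis as intention-to-treat. It will "estimate a logistic regression model that includes clinic fixed effects and month of enrollment", and the model also "controls for baseline participant characteristics that are significantly different between study groups". No significance threshold is given for that last step. For the secondary outcomes the instruction is "We will repeat the primary analyses for each secondary outcome".

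The Outcomes paragraph lists three kinds of secondary outcome:

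- Binary clinic outcomes: "retention in care at 6 months; viral suppression (<50 copies/ml) at 6 and 12 months".
- PDC: "adherence over 6 and 12 months using proportion of days covered (PDC"). No cut-off is given.
- Six-month survey outcomes: "HIV-status disclosure, mental health, internalized stigma, self-esteem, employment and social isolation". No cut-offs or scoring rules are given in the body of the Protocol.

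Under Data collection, the baseline survey is said to cover, among other things, "future outlook, internalized stigma and mental health". Of the six-month survey the Protocol says that "many of the questions administered at baseline will be assessed again". Under Randomization, allocation is 1:1 and follows the baseline survey.

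Under Aim 4, Analysis, the AIM and CSQ-8 scales are analysed by linear regression.

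**The concern.** Two separate difficulties come from the one sentence on secondary outcomes.

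First, ordinary logistic regression needs a yes/no outcome. It suits retention, viral suppression and, if coded yes/no, disclosure and employment. It does not suit mental health, internalised stigma, self-esteem or social isolation if these are kept as scores, and PDC is a proportion. The Protocol gives a cut-off for viral suppression but none for these outcomes.

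Second, the covariate rule decides adjustment by a baseline significance test. In a randomised comparison such a test detects only chance imbalance and says nothing about whether the covariate predicts the outcome. The baseline value of a scale is often the best available predictor of its later value, yet under this rule it is normally left out.

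What is at stake is precision in the outcomes that the Protocol uses to explain how the intervention works. The sample size section also predicts better mental health through reduced internalised stigma.

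**Working it through.** **Inputs.** From the Protocol: 1:1 randomisation after the baseline survey, about 800 men (about 400 per arm), the logistic model and its covariate rule. Assumed, because the Protocol does not state them: the threshold for a significant baseline difference (5%, range 1% to 10%), two-sided 5% testing, and the correlation r between the baseline and six-month values of a scale.

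**1. The plan's own figure.** The 786 participants reproduce. With variance 0.25 in both arms, a difference of 0.10, two-sided 5% and 80% power, n per arm = (1.960 + 0.842)² × 2 × 0.25 / 0.10² = 392.4, rounded up to 393, so 786 in total. This figure concerns the primary outcome only; 400 per arm is carried into step 4.

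**2. How often a baseline score enters the model.** The baseline survey precedes randomisation, so the null hypothesis of no baseline difference is true by design. A test at level a is then significant with probability a, and the covariate is omitted with probability 1 − a.

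| Threshold a | Score enters | Score omitted |
|---|---|---|
| 1% | 1% | 99% |
| 5% | 5% | 95% |
| 10% | 10% | 90% |

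Simulation at the 5% threshold (400 per arm, 10,000 runs per scenario) gave inclusion in 4.8% to 5.2% of runs.

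**3. What omission costs for a continuous score.** Linear adjustment for baseline reduces the outcome variance by the factor 1 − r². Omitting it therefore needs a sample 1/(1 − r²) times as large for the same precision.

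| r (assumed) | 1 − r² | 1/(1 − r²) | Larger sample needed |
|---|---|---|---|
| 0.4 | 0.84 | 1.19 | 19% |
| 0.5 | 0.75 | 1.33 | 33% |
| 0.6 | 0.64 | 1.56 | 56% |

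**4. Power and type I error under the rule.** The simulation used a continuous score analysed linearly, a true effect of 0.2 SD for power and none for type I error, 400 per arm, no dropout, no clinic or month terms, and a 5% threshold.

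| r (assumed) | Power, significance rule | Power, always adjusted | Type I error, significance rule |
|---|---|---|---|
| 0.3 | 81% | 84% | 4.6% |
| 0.5 | 82% | 90% | 4.3% |
| 0.7 | 82% | 98% | 3.7% |

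The rule is slightly conservative: when baseline is found balanced, the unadjusted difference varies less than its standard error implies.

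**5. Which outcomes have a baseline value.** Internalised stigma and mental health are named both in the baseline survey and among the secondary outcomes. Future outlook is in the baseline list but not in the outcome list, although the secondary analyses paragraph mentions future orientation. Self-esteem and social isolation are not named at baseline, and the questionnaires are not shown. No baseline PDC is defined. Baseline retention does not vary, since every man has missed an appointment by more than 28 days and is off ART.

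**The case against.** The strongest reply is that model choice for secondary outcomes belongs in the SAP, which is not at hand, and that repeating the primary analysis may mean only the same framework: intention-to-treat, clinic effects and month of enrolment, with a model suited to the outcome. The Aim 4 use of linear regression shows that the team does not regard logistic regression as universal. For the model mismatch this has real force: analysts would probably fit linear models to scale scores. It does not rescue the covariate rule, which the Protocol itself states and extends to each secondary outcome. An SAP would have to depart from that text to avoid the problem.

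A reader might infer more than the documents support:

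- *That dichotomisation is forced and cut-points will be chosen after the fact.* The Protocol does not mention dichotomising these outcomes, and an SAP could fix cut-offs in advance. For PDC, a fractional logit keeps the logistic link without a cut-off.
- *That the rule drops the baseline value of every secondary outcome.* Collection at baseline is established for two of the listed outcomes only, and PDC has no baseline value.
- *That omission in 95% of cases is a property of the plan.* It depends on a 5% threshold that the Protocol does not state.
- *That a loss from splitting scores adds to the loss from omitting baseline.* A median split of a normal score keeps about 64% (2/π) of the information, but the Protocol proposes no such split. The 19% to 56% figure is for a linear analysis of a continuous score, so the two describe different analyses and cannot be combined.

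It is also fair to say that the consequence is limited: supportive outcomes lose precision, and no false-positive risk is added. At r = 0.3 the power loss is only about 3 points.

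**Conclusion.** The point holds in a limited form. The firm part is the covariate rule: as written, the baseline scores for internalised stigma and mental health are left out of their own outcome models unless chance makes the arms differ, which is about 95% of the time at an assumed 5% threshold (90% to 99% for thresholds of 10% to 1%). For a continuous score with r of 0.4 to 0.6, omission costs the equivalent of a 19% to 56% larger sample. These correlations are assumptions; the Protocol gives none. The cost is precision, not bias or inflated type I error.

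The weaker part is the model mismatch. It is real on a literal reading for scale scores and PDC, and inconsistent with Aim 4, but sensible analysts would probably correct it in practice. It does not touch the primary outcome, 6-month retention or viral suppression.

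**What to change.** Replace the single sentence on secondary outcomes with a rule by outcome type:

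- **Binary secondary outcomes** (6-month retention, viral suppression, and disclosure and employment if coded yes/no): keep the logistic model.
- **Scale scores:** linear regression on arm, clinic and month of enrolment, always including the baseline value of the same measure where it was collected, whatever the baseline tests show. This covers at least internalised stigma and mental health.
- **Any other item repeated from baseline:** include its baseline value in the model on the same terms.
- **PDC:** analyse as a proportion, by mean difference with robust standard errors or by fractional logit, with no baseline PDC term.

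The cost is a few lines in the Protocol, carried into the SAP before outcome data are examined by arm. No new data are needed and the sample size does not change.
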